Patients will be evaluated for safety throughout the study. Adverse events that occur in HGT-SAN-055 and are ongoing at enrollment in HGT-SAN-067 will be captured as ongoing in the HGT-SAN-055 study and also be reported as a concurrent condition in the HGT-SAN-067 eCRFs. Specific safety stopping criteria will be applied and will be based on the types and severity of AEs reported while on-study. These data will be reviewed to inform the decision to discontinue a patient, a dose group, or the study as a whole.

All patients will have an EOS visit 30 (± 7) days following their last administration of HGT-1410 (ie, Month 78). The EOS procedures will include standard clinical laboratory tests (serum chemistry, hematology, and urinalysis) in CSF and blood, protocol specific laboratory testing (eg, anti-rhHNS antibody testing), neurodevelopmental testing, child health questionnaires, and MRI. Use of concomitant medications, therapies, and procedures will be recorded and AEs will be monitored.

All patients will be contacted by telephone or will have a visit for a Final Safety Follow-up, conducted at 30 (± 7) days after the EOS visit (ie, Month 79) to collect updated information on AEs and concomitant medications, therapies, and procedures.

It is anticipated that the IDDD will be used to obtain CSF samples and to administer HGT-1410. However, if a patient's PORT-A-CATH IDDD appears nonfunctional or if its use is precluded on a scheduled day of dosing, site personnel will refer to the PORT-A-CATH Instructions for Use (IFU), which describes the investigation and management of IDDD-related issues with this device. This will include possible partial revision or complete replacement of the PORT-A-CATH IDDD with a SOPH-A-PORT IDDD. For malfunctions involving the SOPH-A-PORT Mini S, site personnel will refer to the SOPH-A-PORT IFU. For either IDDD, a maximum of 2 partial revisions and/or complete replacements are permitted in any 6 month period (including participation in study HGT-SAN-055). If a revision or replacement of the IDDD cannot be scheduled in time to avoid a delay of the next scheduled dose of HGT-1410, or if the patient experiences more than 2 IDDD malfunctions in a 6 month period, HGT-1410 will be

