8.2.1.2 Day 2 (± 2 days) Assessments and Administration of HGT-1410

Patients may be discharged from the clinical site 4 hours after dosing, if deemed stable by the Investigator.

- Physical examination (after Month 54 the full physical examination will be performed at Months 54, 66, and 78. The remainder of the physical examinations will be symptom-directed)
- ECG (performed following IT study drug injection)(after Month 54 performed Q3 months)
- Vital signs
- CSF sample collection (obtained prior to IT study drug injection)
- HGT-1410 IT injection (Day 2 ± 2 days)
- Neurological examination
- Concomitant medications, therapies, and procedures
- AE assessments

The neurological exam should not occur sooner than 4 hours after study drug administration or before the patient has fully recovered from any anesthesia administered for the dosing, whichever occurs later.

8.3 End of Study/Early Termination Procedures: Month 79

Patients who complete the study or who discontinue prior to the end of the study, will have EOS assessments performed 30 (± 7 days) after their last dose of HGT-1410.

Patients who discontinue or are withdrawn prior to study completion will be asked to participate in the EOS procedures at the time of discontinuation. Participation in these EOS procedures will be strongly encouraged, but is voluntary for those patients electing to discontinue from the study. Note: Patients will have the IDDD removed when they discontinue from the study, unless the patient is continuing to receive treatment through another mechanism (eg, expanded access, commercially available).

- Physical examination
- Height and weight
- Head circumference
- Visual and hearing assessment
- ECG
- Vital signs
- Hematology
- Serum chemistries
- Urinalysis
- Urine GAG, including heparan sulfate and heparan sulfate derivatives
- Anti-rhHNS antibody testing (serum and CSF)
- MRI of the head (unless performed at Month 78)
- CSF sample collection (unless performed at Month 78)
- Neurological examination
- Full neurodevelopmental testing, including VABS-II
- Children's Sleep Habits Rating Scale
- CHQ-50
- CHQ-87
- Infant toddler QoL Questionnaire
- Concomitant medications, therapies, and procedures
- AE assessments

All patients who discontinue the study early will have their IDDD removed.

Patients who withdraw or discontinue after having received fewer than 3 IT injections will not need to complete the EOS visit.

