Patients who withdraw or discontinue from the study after having received 3 or more IT injections, will be asked to complete the EOS visit and undergo all the scheduled assessments.

8.4 Safety Follow-up (by Telephone or Visit) Month 80

Patients who complete the study or withdraw early will have a safety follow-up telephone call or visit 30 Days (± 7 days) after the last study visit. This will assess:

- Concomitant medications, therapies, and procedures
- AE assessments

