10.6 Efficacy, Safety, and Pharmacodynamic Evaluations

10.6.1 Primary Analyses

10.6.1.1 Safety Analysis

In general, safety assessments will be based on all assessments post-baseline. The assessment of safety will be based primarily on the frequency of AEs, and on the frequency of clinically notable abnormal vital sign and laboratory values. Changes from baseline will be calculated by subtracting the baseline value from the post-baseline value.

All enrolled patients who had an IDDD surgical procedure and/or received administration of HGT-1410 will be included in the safety analysis.

Adverse events will be recorded throughout the study and at early termination. Adverse events and medical conditions will be coded using the Medical Dictionary for Regulatory Activities (MedDRA).

Adverse events will be summarized by presenting, for each dose group, the number and percentage of patients having any AE, having an AE in system organ class, and having each individual AE. In addition, those events which resulted in death or were otherwise classified as serious will be presented in a separate listing. The incidence of treatment-emergent adverse events, defined as all AEs from the time of the surgery for IDDD implantation to the last follow up contact, ie, 30 days after the last HGT-1410 administration, (new or worsened from baseline) will be summarized by system organ class, severity, type of adverse event and relationship to trial medication/procedure.

Treatment-emergent AEs deemed related to HGT-1410 administration will be summarized separately.

IDDD and procedure-related AEs will be summarized within system organ class by preferred term. IDDD and procedure-related AEs will be tabulated by severity (mild, moderate, severe) and degree of relatedness. Separate tabulations will be provided for adverse events related to the IDDD, device surgical procedure (including post-implant infections) and IT administration process. These summaries will be presented by device and overall, as appropriate.

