Primarily main sites will be utilized; however, the sponsor and investigator will consider the feasibility of transitioning the patient's IT dosing to local sites to reduce the burden imposed by travel. At Month 18 (12 months after study start), patients that already received IT dosing at the main site may be eligible to transfer to a local site if in the opinion of the investigator there are no safety or medical concerns precluding this transition. Subsequent IT injections of HGT-4110 may be performed at either the main site or the local site. The local sites will be selected and approved by the sponsor, and the patient must have no safety or medical issues that would preclude transitioning to a local site (Note: the main site may serve as a local site as needed; and in this case, the main site will follow the assessments scheduled for a local site). The qualification requirements for physicians at local sites will be identical to those for the main sites. Local sites will be trained if inexperienced with IT administration via an IDDD. Patients will be discharged a minimum of 4 hours after dosing and when deemed clinically stable by the investigator. Dosing by IT injection may take place at the main site, rather than local site, if scheduled study assessments include MRI and cognitive assessments. Patients must review and agree to written informed consent/assent from the local site to participate in study procedures to be conducted at the local site prior to the conduct of these procedures.

In order to maintain a nomenclature system based on study chronology across the original HGT-SAN-055 study and this extension study, the Baseline Visit for this extension study will be considered to be the day the patient received their first IT dose of HGT-1410 in Study HGT-SAN-055. The HGT-SAN-055 EOS assessment information will provide the screening/start of study information for patients who continue into the HGT-SAN-067 extension study. Note: HGT-SAN-055 EOS data must be recorded in the context of the HGT-SAN-055 trial, and a copy of those data can be used for HGT-SAN-067 screening. Once eligibility is confirmed, informed consent (and assent, if applicable), provided by the patient's parent(s)/legally authorized representative(s), must be obtained prior to performing any HGT-SAN-067 study-related procedures. Informed consent may be obtained anytime from

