It is anticipated that the IDDD will be used to obtain CSF samples and to administer HGT-1410. However, if a patient's PORT-A-CATH IDDD appears nonfunctional or if its use is precluded on a scheduled day of dosing, site personnel will refer to the PORT-A-CATH Instructions for Use (IFU), which describes the investigation and management of IDDD-related issues with this device. This will include possible partial revision or complete replacement of the PORT-A-CATH IDDD with a SOPH-A-PORT IDDD. For malfunctions involving the SOPH-A-PORT Mini S, site personnel will refer to the SOPH-A-PORT IFU. For either IDDD, a maximum of 2 partial revisions and/or complete replacements are permitted in any 6 month period (including participation in study HGT-SAN-055). If a revision or replacement of the IDDD cannot be scheduled in time to avoid a delay of the next scheduled dose of HGT-1410, or if the patient experiences more than 2 IDDD malfunctions in a 6 month period, HGT-1410 will be administered via lumbar puncture (LP). If implantation of a replacement IDDD is not possible, investigational drug may be administered by LP for a maximum of 12 successive monthly doses. At that point, a safety discussion needs to take place between the investigator and the sponsor to determine the risk/benefit of further dosing by LP.

If there is no significant safety risk in the opinion of the investigator, a non-functional IDDD may be left in situ for up to 3 months.

Patients who discontinue or are withdrawn before receiving 3 monthly IT injections will not have to undergo the EOS evaluations but will have their IDDD removed.

If a patient discontinues, or withdraws from the study, or the study is stopped by the sponsor, the IDDD will be removed as part of the EOS Procedures.

An overview of the study appears in the Schedule of Events ([Appendix 1](#)).

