7.22 Adverse Events

7.22.1 Definitions of Adverse Events and Serious Adverse Events

7.22.1.1 Adverse Event

An AE is any noxious, pathologic, or unintended change in anatomical, physiologic, or metabolic function as indicated by physical signs, symptoms, or laboratory changes occurring in any phase of a clinical study, whether or not considered study drug-related. This includes an exacerbation of a pre-existing condition. Once the informed consent is signed and dated, any adverse event prior to the start of study drug must be reported.

AEs include:

- Worsening (change in nature, severity, or frequency) of conditions present at the onset of the study
- Intercurrent illnesses
- Drug interactions
- Events related to or possibly related to concomitant medications
- Abnormal laboratory values (this includes significant shifts from baseline within the range of normal that the investigator considers to be clinically important)
- Clinically significant abnormalities in physical examination, vital signs, and weight

Throughout the study, the investigator must record all AEs on the AE eCRF, regardless of the severity or relationship to study drug. The investigator should treat patients with AEs appropriately and observe them at suitable intervals until the events stabilize or resolve. AEs may be discovered through observation or examination of the patient, questioning of the patient, complaint by the patient, or by abnormal clinical laboratory values.

In addition, AEs may also include laboratory values that become significantly out of range. In the event of an out-of-range value, the laboratory test should be repeated until it returns to normal or can be explained and the patient's safety is not at risk.

All AEs should be recorded with causality assessment.

The information presented below is intended to provide issues to consider for AEs associated with intrathecal injections of HGT-1410. In general, these AEs can be classified as follows:

- Adverse events due to systemic exposure to HGT-1410 caused by the drug diffusion from the CSF to the peripheral circulation;
 - Adverse events related to the direct delivery of HGT-1410 to the intrathecal CSF space and meninges, and subsequent diffusion into brain parenchyma, via an intrathecal route
 - IDDD-related AEs
-

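### The treatment-emergent AE window in Section 10.6.1.1 ends on two dates that disagree: day 30 after the last dose, and the last safety contact, which the schedule puts at about day 60

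*Protocol*

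**What the plan says.** Section 10.6.1.1 gives both ends of the TEAE window in one sentence. TEAEs are "defined as all AEs from the time of the surgery for IDDD implantation" and the window runs "to the last follow up contact, ie, 30 days after the last HGT-1410 administration", limited to events that are new or worse than baseline. TEAE incidence is to be summarised by system organ class, severity, event type and relationship to trial medication or procedure. TEAEs judged related to HGT-1410 get a separate summary.

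The visit schedule is set elsewhere in the protocol:

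- **EOS visit.** Section 4.1 places it 30 (±7) "days following their last administration of HGT-1410 (ie, Month 78". Section 8.3 agrees on the interval: "Patients who complete the study or who discontinue prior to the end of the study, will have EOS assessments performed" 30 (±7) days after the last dose. Footnote e of Table A1-1 says the same for completers.
- **Final safety contact.** Section 8.4: "Patients who complete the study or withdraw early will have a safety follow-up telephone call or visit 30 Days" (±7) after the last study visit. Section 4.1 and footnote f of Table A1-1 count it from EOS. AEs are collected at this contact.
- **Device removal.** Section 4.1 says that if a patient discontinues or withdraws, or the sponsor stops the study, "the IDDD will be removed as part of the EOS Procedures". Sections 7.13.4 and 8.3 exempt patients who go on receiving treatment by another mechanism.

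**The concern.** The sentence treats the last follow-up contact and day 30 after the last dose as the same date, but day 30 is when the EOS visit falls due. The last contact is a further month away. A programmer who follows the named event and one who follows the day count will produce different TEAE tables from the same data.

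The disputed month follows removal surgery in patients who stop treatment. Section 7.22.1.3 of the Amendment 6 text lists anaesthesia complications, excessive bleeding and post-operative infection among device-surgery AEs, and some of these can appear only after removal. EOS may also take place on days 31 to 37, in which case a literal day-30 cut-off would exclude even events on the day of removal.

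What is at stake is specific. For AEs as a whole, Section 10.6.1.1 assigns the breakdown by severity and relationship to the TEAE summary. The any-AE summary is described only by any event, system organ class and individual event. Drug-related events get a separate summary only as TEAEs. The cut-off therefore decides which late events reach those tables.

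**Working it through.** **Inputs**

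- Stated end of window: 30 days after the last dose, described as the last follow-up contact (Section 10.6.1.1).
- Last dose to EOS: 30 (±7) days, so day 23 to 37 (Sections 4.1 and 8.3).
- EOS to final safety contact: 30 (±7) days, so 23 to 37 days (Sections 4.1 and 8.4; Table A1-1, footnote f).

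**Step 1: try to reproduce the plan's 30 days.** Day of last contact = (last dose to EOS) + (EOS to final contact).

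- Nominal: 30 + 30 = 60 days.
- Earliest: 23 + 23 = 46 days.
- Latest: 37 + 37 = 74 days.

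For a patient with an EOS visit on schedule, no combination of visit windows gives day 30. Day 30 lies within the EOS range (23 to 37) and outside the last-contact range (46 to 74).

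**Step 2: length of the disputed period.** Days of AE collection after day 30 = day of last contact − 30.

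- Nominal: 60 − 30 = 30 days.
- Range: 46 − 30 = 16 to 74 − 30 = 44 days.

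**Step 3: in proportion.**

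- Of follow-up after the last dose: 30/60 = 50%, with range 16/46 = 35% to 44/74 = 59%.
- Of a completer's whole time on study: 30/(6 × 365) = 1.4% with the 6-year duration of Amendment 6, or 30/(8 × 365) = 1.0% with up to 8 years under Amendment 7. The share is larger for early withdrawals.
- With at most 12 patients, one patient added to a TEAE row changes the overall percentage by at least 1/12 = 8.3 points.

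**Step 4: which outputs depend on the cut-off** (Sections 10.6.1.1 and 3.1).

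- Dependent: the TEAE incidence summary (including severity and relationship) and the HGT-1410-related TEAE summary.
- Not stated to be limited to TEAEs: the any-AE summary by dose group, the listing of deaths and other serious events, the IDDD, device-surgery and IT-administration tables (which carry their own severity and relatedness breakdown), and the listings of all safety data.
- The primary endpoint in Section 3.1 is AEs by type and severity, without a TEAE restriction.

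**Step 5: does the schedule differ elsewhere?** Month labels differ: Section 4.1 has EOS at Month 78 and follow-up at Month 79, while Sections 8.3 and 8.4 have Months 79 and 80. The 30 + 30 day intervals agree throughout, so the arithmetic is unaffected. Section 4.1 of Amendment 7 keeps the same intervals.

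**The case against.** The strongest reply is that the sentence names the last follow-up contact first. Read by that event, the window already covers the whole of follow-up, and only the gloss is wrong. That is fair: the defect is a contradiction with two possible cut-offs, and no exclusion is firmly fixed. It does not remove the problem, because the day count is the more directly programmable half of the sentence.

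Removal at EOS is also not universal. Patients who continue treatment by another mechanism keep the device, and removals or revisions during treatment fall inside the window on either reading. The documents give no data on how many complications would fall in the disputed month. All of this limits the size of the effect.

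A reader might infer more than the text supports, in three ways:

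- **That late AEs drop out of the primary endpoint.** They do not. The endpoint is AEs in general, collection runs to the final contact, and the other AE outputs are not stated to be limited to TEAEs. Explant complications belong in the device and procedure tables in any case.
- **That events after implantation count as baseline**, because "the Baseline Visit for this extension study will be considered to be the day the patient received their first IT dose" in HGT-SAN-055. Section 4.1 gives that definition to keep a common study chronology and does not call it the AE reference, while Section 10.6.1.1 expressly counts events from implant surgery. The exclusion is not stated.
- **That events are counted twice**, because 067 consent is allowed from Week 20 of 055 and "Once the informed consent is signed and dated, any adverse event prior to the start of study drug must be reported". Section 4.1 records 055 events still ongoing at enrolment as concurrent conditions in 067. New events between early consent and the 055 EOS visit are a narrow data-management matter, and nothing in the text shows duplicate tabulation.

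**Conclusion.** The end of the TEAE window is wrong as written. Section 10.6.1.1 equates two dates that the protocol's own schedule puts about 30 days apart (16 to 44 with the visit windows). The effect is confined to the TEAE summary by severity and relationship and to the HGT-1410-related TEAE summary. It is a small part of total observation time but about half of follow-up after the last dose.

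This rests on three assumptions. First, the patient has an EOS visit at the scheduled time. Section 8.3 excuses patients with fewer than 3 injections from EOS, and if their last visit was a dosing visit, Section 8.4 would put their last contact near day 30. Second, the tables not described as treatment-emergent really are unrestricted. Third, the wording is still in force: it comes from Amendment 6, and Section 10 of Amendment 7 is not in the text at hand, so its persistence cannot be confirmed.

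**What to change.** In Section 10.6.1.1, delete the gloss that places the last follow-up contact 30 days after the last HGT-1410 administration. State that the TEAE window ends at the final safety follow-up contact, 30 (±7) days after EOS, or after the last study visit where no EOS visit is held. Check whether Amendment 7 Section 10.6.1.1 keeps the wording, correct it there too, and use the same definition in the SAP.

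The cost is a wording change and a changed date rule in programming. The protocol already collects AEs and their onset dates through that contact, so no visit or assessment is added. The only downside is slightly higher TEAE counts.
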